### 3.1.2 Overall Design and Control Methods

[figure not shown]
This is a trial investigating the safety, tolerability, pharmacokinetics and pharmacodynamics of FE 204205 in cirrhotic patients with portal hypertension. The trial is divided in two parts:

Part 1 is an open-label investigation of safety, tolerability, pharmacokinetics and pharmacodynamics of increasing intravenous doses of FE 204205 and will include 6 patients. Dosing will take place in a staggered fashion, with one patient completing dosing before the next patient will be dosed (i.e. with at least 3 days between administration of the first dose in one patient and the first dose in the next patient). Systemic and portal haemodynamics will be assessed by pulmonary artery and hepatic vein catheterization on Day 3. Each patient will receive three ascending doses of FE 204205, given once daily as 2-hour infusions on three consecutive days. Dose escalation on Days 2 and 3 will only commence provided that the increase in mean arterial

pressure from baseline is  $<15$  mmHg, absolute mean arterial pressure  $\leq 120$  mmHg, systolic blood pressure  $\leq 160$  mmHg, diastolic blood pressure  $\leq 100$  mmHg, and heart rate  $\geq 55$  beats per minute at any of the vital signs assessments during the 4 hours after start of infusion on the previous day. If these criteria are not met, the same dose will be administered the next day. If the increase of dose results in non-tolerable effects, the preceding tolerated dose will be reverted to for the remaining administrations in that patient.

For the first 3 patients, the initial treatment given on Day 1 will be a single dose of 0.01 mg FE 204205 followed by planned doses of 0.025 mg FE 204205 on Day 2 and 0.05 mg FE 204205 on Day 3. For the remaining 3 patients, the planned single doses are 0.025 mg FE 204205 on Day 1, 0.05 mg FE 204205 on Day 2 and 0.1 mg FE 204205 on Day 3. After the first 3 patients have completed all Visit 2 assessments, a Safety Review Committee (SRC) will evaluate the preliminary safety, tolerability, and pharmacodynamics data of the FE 204205 and will decide if the dosing regimen can be increased as planned, or if a modified (lower) dose regimen should be applied (see Figure 3-3).

6 subjects divided in 2 cohorts (3+3):

**Figure 3-3:** Suggested trial design for the 6 patients in Part 1.

\*SRC = Safety Review Committee.

HVPG will be the primary pharmacodynamic parameter and assessments will be performed before, during, and immediately after the intravenous administration on Day 3. Patients will be confined to the clinic during the treatment period and will be carefully monitored for adverse events and effects on systemic haemodynamics.

A Safety Review Committee (SRC) will evaluate the safety, tolerability, and pharmacodynamics of the compound after the completion of Part 1 to recommend what dose of FE 204205 to evaluate in Part 2.

Part 2 is a placebo controlled, double-blind, randomised investigation evaluating the effects of a single dose of FE 204205 on portal haemodynamics and will include 16 patients receiving FE 204205 and 4 patients receiving placebo. Each patient will receive a 2-hour intravenous infusion of the maximum tolerated dose of FE 204205 as defined in Part 1, or placebo, on Day 1. Systemic and portal haemodynamics will be assessed by pulmonary artery and hepatic vein catheterization. HVPG will be the primary pharmacodynamic parameter and assessments will be performed before,

during, and immediately after the intravenous administration. Patients will be confined to the clinic during the treatment period and will be carefully monitored for adverse events and effects on systemic haemodynamics.

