In Part 1, provided that the dose on the preceding day is regarded safe and tolerable, the subsequent dose can be increased. The planned doses for the first 3 patients are 0.01 mg FE 204205 on Day 1, 0.025 mg FE 204205 on Day 2 and 0.05 mg FE 204205 on Day 3. After the SRC has evaluated the preliminary data on safety, tolerability and pharmacodynamics of FE 204205 from the first 3 patients, the planned doses for the remaining 3 subjects may be increased to maximum 0.025 mg FE 204205 on Day 1, 0.05 mg FE 204205 on Day 2 and 0.1 mg FE 204205 on Day 3 (see protocol section 3.4). Dose escalation in the subject on Days 2 and 3 will only commence provided that the increase in mean arterial pressure from baseline is  $< 15$  mmHg, absolute mean arterial pressure  $\leq 120$  mmHg, systolic blood pressure  $\leq 160$  mmHg, diastolic blood pressure  $\leq 100$  mmHg, and heart rate  $\geq 55$  beats per minute at all of the vital signs assessments during the 4 hours after start of infusion on the previous day. If these criteria are not met, the same dose will be administered the next day. If the increase of dose results in non-tolerable effects, the preceding tolerated dose will be reverted to for the remaining administration in that subject. The highest planned dose of 0.1 mg infused over 2 hours ( $= 0.05$  mg/hr) corresponds to the infusion rate applied for the dose level of 0.3 mg IV infused over 6 hours ( $= 0.05$  mg/hr) given to healthy subjects and is expected to not exceed the exposure in healthy subjects by means of  $C_{max}$  (expected  $C_{max}$ : approximately 3 ng/mL). At this dose level in healthy subjects (0.05 mg/hr IV over 6 hours), the mean arterial pressure increased (max. mean increase of +14 mmHg) and the pulse decreased. The dose level was safe and well tolerated in healthy subjects, as were dose levels up to 3 times higher (highest dose level studied in healthy subjects was 0.9 mg infused over 6 hours = 0.15 mg/hr).

The highest planned dose of 0.1 mg infused over 2 hours ( $= 0.05$  mg/hr) that may be reached on Day 3 is the same that was assigned to patient █ on Day 1. However, this dose level will only be reached in a patient in Part 1 who has already tolerated two lower dose levels of FE 204205 on Day 1 and Day 2 and met the dose escalation criteria above.

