The chosen dose increments between dose levels (increasing by a factor of 2.5 from the starting dose, then maximum increase of factor 2 for the subsequent doses) are lower and thus more conservative than the ones used in the trials with healthy subjects, where a factor of  $\sim 3$  was applied for the respective dose range from 0.005 mg/hr to 0.05 mg/hr.

In Part 2 each patient will receive a 2-hour intravenous infusion of the dose of FE 204205 selected by the SRC, or placebo, on Day 1. The SRC will select the dose based on incidence and frequency of adverse events, safety laboratory data, ECG, systemic and portal haemodynamic parameters. The dose selected will be the maximum tolerated dose (MTD) or a lower dose. The MTD is defined as the dose level below the dose where one or more stopping criteria, as confirmed by a second measurement, are met in at least two subjects in Part 1.

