#### **4.5 Stopping Criteria**

The infusion will be interrupted and may be adjusted in the subject if any of the below stopping criteria occur, and halted for evaluation by the SRC when one or more criteria, as confirmed by a second measurement, are met in at least two subjects receiving the same treatment.

- Systolic blood pressure increased by 50% or more from the baseline and reaching >160 mmHg
- Systolic blood pressure 180 mmHg or higher
- Diastolic blood pressure 105 mmHg or higher
- Mean arterial pressure 130 mmHg or higher
- Heart rate 45 beats per minute or lower
- Signs or symptoms of mesenteric or peripheral ischemia, or hypertensive crises.

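### The Part 1 dose-escalation rule says *any* vital-signs assessment in the synopsis and 3.1.2 but *all* in 3.5.4; *all* is clearly meant and should appear in all three places

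*Combined protocol and SAP*

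**What the plan says.** The rule for raising the dose within a patient on Days 2 and 3 of Part 1 appears three times. The five limits are the same each time: rise in mean arterial pressure (MAP) below 15 mmHg, MAP at most 120 mmHg, systolic pressure at most 160 mmHg, diastolic pressure at most 100 mmHg, and heart rate at least 55 beats per minute.

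- Synopsis (Methodology) and section 3.1.2: the limits must hold "at any of the vital signs assessments during the 4 hours after start of infusion on the previous day".
- Section 3.5.4: the limits must hold "at all of the vital signs assessments during the 4 hours after start of infusion on the previous day".

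Section 3.1.2 then states what follows from a failure: "If these criteria are not met, the same dose will be administered the next day". Section 3.5.4 describes the planned steps as "increasing by a factor of 2.5 from the starting dose, then maximum increase of factor 2 for the subsequent doses". It also makes an increase possible only "provided that the dose on the preceding day is regarded safe and tolerable".

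Section 4.5 sets separate stopping criteria for the infusion itself: "The infusion will be interrupted and may be adjusted in the subject if any of the below stopping criteria occur".

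**The concern.** Staff apply this rule at the bedside, and its statements differ in the one word that fixes how strict it is. Under *all*, a single reading outside the limits holds the dose. Under a literal *any*, a single reading inside the limits releases it, and the first reading, 5 minutes into the infusion, could be enough. The weaker word stands in the synopsis and in the main design section, while the clear word stands only in the dose rationale. No clause in the available text says which governs.

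The drug is a vasoconstrictor given to patients with cirrhosis for the first time, and the decision is whether the next day's dose doubles or more. If the literal reading were applied, a patient with a marked pressure response could receive a higher dose although 3.5.4 would hold it.

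**Working it through.** The plan gives no figure to reproduce here. The check compares the texts, counts what the rule covers, and asks whether another rule would catch the same patient.

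**1. Decisions covered (Table 5-1).** 6 patients × 2 escalation days = 12.
- Patients 1–3: 0.025/0.01 = 2.5-fold (3 decisions), then 0.05/0.025 = 2-fold (3 decisions).
- Patients 4–6: 0.05/0.025 = 2-fold (3 decisions), then 0.1/0.05 = 2-fold (3 decisions).
- Total: 3 steps of 2.5-fold and 9 of 2-fold.

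**2. Readings in the window (section 7.1.2, Table 6-1).**
- During the infusion: 5, 10, 15, 20, 25, 30, 40, 50, 60, 75, 90, 105 and 120 minutes = 13.
- After it ends: 135, 150, 180 and 240 minutes = 4.
- Total: 17.

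Section 7.1.10 lists only 7 times within 4 hours (0.25, 0.5, 1, 1.5, 2, 3 and 4 hours) but refers back to 7.1.2. The wording conflict is the same on either count. Under *all*, 17 of 17 must be within limits. Under a literal *any*, 1 of 17 suffices and 16 may be outside.

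**3. Which wording is intended.** Three pieces of text point to *all*.
- The sentence in 3.1.2 that repeats the dose after a failure would have almost no use if one good reading passed the patient.
- Section 3.5.4 uses *all* outright.
- Section 3.5.4 then defends the 0.1 mg dose by noting that only patients who tolerated two lower doses and satisfied the criteria it has just set out will reach it. Those criteria are the *all* version.

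**4. Whether the stopping criteria replace the rule.** Take an illustrative patient with baseline 115/70 mmHg and later readings of 145/85 mmHg, heart rate 50 and no ischaemic symptoms. These values are assumed, with MAP = DBP + (SBP − DBP)/3.
- Baseline MAP: 70 + 45/3 = 85 mmHg.
- Later MAP: 85 + 60/3 = 105 mmHg, a rise of 20 mmHg.
- Systolic rise: 145/115 − 1 = 26%.

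| Quantity | Escalation needs | Section 4.5 stops at | Example | Escalation limit | Stopping criterion |
|---|---|---|---|---|---|
| MAP rise, mmHg | < 15 | no limit | 20 | fails | none exists |
| MAP, mmHg | ≤ 120 | ≥ 130 | 105 | passes | not met |
| Systolic, mmHg | ≤ 160 | ≥ 180, or up ≥ 50% and > 160 | 145 (+26%) | passes | not met (both) |
| Diastolic, mmHg | ≤ 100 | ≥ 105 | 85 | passes | not met |
| Heart rate, bpm | ≥ 55 | ≤ 45 | 50 | fails | not met |

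Two of the five escalation limits fail, and none of the five numeric stopping criteria is met. The systolic criterion is the only one that refers to baseline: "Systolic blood pressure increased by 50% or more from the baseline and reaching >160 mmHg". The action in the individual patient is to interrupt the infusion, whereas 4 of the 17 readings fall after it has ended. For this patient *all* holds the dose. A literal *any* would permit the increase if one early reading was within limits.

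**5. Whether the MAP-rise limit could be reached.** In healthy subjects at 0.05 mg/hr over 6 hours, 3.5.4 reports that "the mean arterial pressure increased (max. mean increase of +14 mmHg) and the pulse decreased". That is 15 − 14 = 1 mmHg under the limit. The infusions that feed an escalation decision run at 0.005 to 0.025 mg/hr over 2 hours, so at most half that rate (0.025/0.05), and the rise may be smaller.

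**The case against.** The strongest reply is that nobody would apply the literal reading. In a clause allowing escalation only on condition that limits hold, *any* is ordinary usage for *any and every*. The repeat-dose sentence makes sense only on that reading, and 3.5.4 says *all* in terms. To go wrong, staff would have to rely on one early reading, pass over later readings such as a 20 mmHg rise with a heart rate of 50, overlook 3.5.4, and still regard the dose as safe and tolerable. This largely stands, and it is why the point is of low severity. It does not remove the point: a safety rule should not depend on inferring intent when another section already states it correctly.

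Other protections also remain: the stopping criteria, return to the preceding tolerated dose (3.1.2), pausing or slowing the infusion (section 6), withdrawal (4.4) and Safety Review Committee review (3.4). They rest on judgement, act on looser limits or act later. None is an equivalent numeric rule for the next day's dose.

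A reader might go further in three ways that the documents do not support.
- *The design allows unsafe escalation.* It does not; the intended rule is strict and one section states it plainly.
- *The 1 mmHg margin shows that breaches will be common.* It compares a group mean in healthy subjects, at a higher rate and over a longer infusion, with a limit for individual patients. The available text gives no rise for cirrhosis at these doses.
- *The rule should also name scheduled and additional readings.* Section 3.5.4 already covers all assessments on its plain words, and 7.1.2 counts extra safety readings as vital-signs assessments. If the addition were not redundant, it would make one unconfirmed, unscheduled reading decisive. That is a separate and debatable choice.

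**Conclusion.** The inconsistency is real: two statements of the rule say *any* and one says *all*, with identical limits and window. *All* is clearly intended. The literal alternative would loosen the requirement from 17 of 17 scheduled readings to 1 of 17, across 12 planned decisions to raise the dose 2- to 2.5-fold, and the stopping criteria would not reliably catch the difference.

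This is a low-severity wording correction to a safety rule, not a design failure. The documents give no basis for estimating how often decisions would differ, and if staff read *any* as *each* the difference is nil. The example in the working shows that the wordings can diverge; it does not show that they will.

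The statement that nothing settles which text governs applies to the available text only. The opening of 3.5.4 and Figure 3-3 are not shown, and the committee's working procedure and the separate administration instruction are not part of the documents.

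**What to change.** In the synopsis (Methodology) and section 3.1.2, replace *any* with *all*, so that both match 3.5.4. Leave 3.5.4 unchanged and add no further qualifier.

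The edit is one word in two places. It changes no threshold, procedure, sample size or analysis. It does need a protocol amendment under section 12.1, agreed by the sponsor and the investigator and possibly submitted to the ethics committee and authorities. It is best made before the next Part 1 patient is dosed.

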### **3.5.7 Withdrawal Criteria**

The subject should be withdrawn if any signs of serious, or unexpected and unacceptable treatment emergent AEs occur, and may be withdrawn if the inclusion or exclusion criteria are violated during the conduct of the study. The subjects have the right to withdraw at any time for any reason without justification. In addition, a number of stopping criteria are defined, related to cardiovascular parameters (see Section 4.5).

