#### **4.4 Withdrawal Criteria**

The Investigator has the right and obligation to withdraw a subject should any signs of serious, or unexpected and unacceptable treatment emergent AEs occur. Furthermore, a subject may be withdrawn from the study if the inclusion or exclusion criteria are violated during the conduct of the study.

Both the Investigator (with regard to his/her participation) and Ferring, reserves the right to discontinue the study at any time for safety reasons, such as signs of unacceptable adverse reactions, or mortality, or any other reasons jeopardising the justification of the study. Such a termination will be implemented in a time frame that is compatible with the subject's well-being. If the study is prematurely terminated or suspended, the investigator should promptly inform the subjects and assure appropriate follow-up and treatment if required. Ferring Pharmaceuticals A/S will notify the Regulatory Authorities of any plans to terminate the study, and the Investigator will notify the Independent Ethics Committee (IEC).

The subjects have the right to withdraw from the trial at any time for any reason, without the need to justify their decision. For any discontinuation, the Investigator will obtain all the required details and document the date of the premature termination and the main reason in the eCRF. If possible, follow-up assessments should be performed for subjects who are withdrawn after start of infusion.

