#### Expedited Reporting

All AEs that are serious, unexpected and considered related to the IMP judged by either the Investigator or Ferring require expedited reporting. The expectedness is assessed by Ferring according to the Investigator's Brochure.

All available information relevant to the evaluation of the SAE will be reported. SAEs will be considered reportable regardless of whether or not the IMP was used in accordance with the provisions in the Protocol and/or the Investigator's Brochure. AEs that are serious but expected (related and/or unrelated to the IMP) are subject to expedited reporting in accordance with local requirements.

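### Part 1's same-dose rule has no exception for the first patient who meets a numeric stopping criterion, and the escalation check itself is worded in two ways

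*Combined protocol and SAP*

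**What the plan says.** **Escalation check (synopsis, Methodology; 3.1.2; 3.5.4).** Escalation on Days 2 and 3 requires a rise in mean arterial pressure (MAP) below 15 mmHg, MAP ≤120, systolic pressure (SBP) ≤160, diastolic pressure (DBP) ≤100 and heart rate (HR) ≥55. These are judged over the 4 hours after the start of the previous day's infusion. The synopsis and 3.1.2 apply the limits at *any* of the assessments; 3.5.4 says *all*.

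**When the check fails.** "If these criteria are not met, the same dose will be administered the next day".

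**Stepping back.** "If the increase of dose results in non-tolerable effects, the preceding tolerated dose will be reverted to" for that patient's remaining administrations.

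**Stopping criteria (4.5).** For the individual: "The infusion will be interrupted and may be adjusted in the subject if any of the below stopping criteria occur". Dosing is "halted for evaluation by the SRC when one or more criteria, as confirmed by a second measurement, are met in at least two subjects"; both must be on the same treatment.

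**Withdrawal.** Section 4.4: "The Investigator has the right and obligation to withdraw a subject should any signs of serious, or unexpected and unacceptable treatment emergent AEs occur". Section 3.5.7, also headed as withdrawal criteria, adds that cardiovascular stopping criteria are defined and points to 4.5.

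**Stagger (3.1.2).** "Dosing will take place in a staggered fashion, with one patient completing dosing before the next patient will be dosed". The synopsis asks only that the first two patients' first doses fall on separate days.

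**Discretionary measures.** Unscheduled Safety Review Committee (SRC) meetings (3.4), an SRC-modified regimen (5.1.1.1) and pausing or slowing the infusion (section 6) are all optional.

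**The concern.** A stopping criterion marks a reaction serious enough to interrupt the infusion. Section 3.5.4 also uses these criteria to define the maximum tolerated dose. A reader would expect the next-day rule for that patient to be a lower dose or none. Instead, the only mandatory dosing sentence that reaches a first stopping event without a prior dose increase is the one written for patients who narrowly miss escalation. A MAP rise of 15 mmHg and a heart rate of 45 get the same instruction.

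This is the first study of the drug in patients with cirrhotic portal hypertension, and a Day 3 repeat would be given during catheterization under sedation. The safe outcome then depends on someone departing from the written default.

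The *any*/*all* difference leaves two texts for one safety check.

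**Working it through.** The plan gives no figure on this point, so the check sets the rules side by side.

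**1. Can a patient meet a numeric stopping criterion and still pass the check?** (Limits from 3.5.4 and 4.5.)

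| Variable | Passes escalation check | Meets stopping criterion | Overlap |
|---|---|---|---|
| SBP, relative | ≤160 | ≥50% rise and >160 | none |
| SBP, absolute | ≤160 | ≥180 | none |
| DBP | ≤100 | ≥105 | none |
| MAP | ≤120 | ≥130 | none |
| HR | ≥55 | ≤45 | none |

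Five of five lie outside. If the limits must hold at all assessments, any numeric stop recorded at a vital-signs assessment in the 4-hour window fails the check and brings in the same-dose sentence.

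**2. Does another mandatory rule set the next dose for the first such patient?**

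- *Step-back sentence:* it needs an increase of dose, so it cannot apply after Day 1 or after a Day 2 dose that was not raised. After a raised Day 2 dose it can apply, but intolerance is not tied to 4.5, so two sentences compete: 0.025 or 0.01 mg on Day 3 for patients 1-3, and 0.05 or 0.025 mg for patients 4-6.
- *Interruption under 4.5:* it acts on the infusion in progress.
- *SRC halt under 4.5:* it needs two patients. Under 3.1.2, first doses are at least 3 days apart and each patient finishes before the next starts, so a later patient cannot trigger the halt before the first patient's Day 3 dose. The synopsis stagger is looser.
- *Withdrawal under 4.4:* mandatory, but tied to adverse events and not to the numeric limits.
- *Sections 3.4, 5.1.1.1 and 6:* permissive.

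**3. Ceiling on repeat infusions (Table 5-1).** Planned infusions: 6 × 3 = 18. With confirmed criteria, the first patient on a Day 1 dose is 1 of 6 if the same treatment means the drug. It is at most 2 of 6 if it means the dose level (0.01 mg in patients 1-3, 0.025 mg in patients 4-6). Each could have repeats on Days 2 and 3.

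- 1 × 2 = 2; 2/18 = 11%
- 2 × 2 = 4; 4/18 = 22%

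**4. How likely is a Day 1 stop?** Section 3.5.4 gives a largest mean MAP rise of 14 mmHg in healthy subjects at 0.05 mg/hr. Reaching 130 with that rise needs a pre-dose MAP of 130 − 14 = 116, although an individual's rise may exceed the mean. Day 1 rates are 0.005/0.05 = 10% and 0.0125/0.05 = 25% of that rate.

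That comparison is lenient. Section 1.1 puts the maximal blood-pressure effect at 0.1 mg over 6 hours, or 0.1/6 = 0.0167 mg/hr. Against that rate, Day 1 is 0.005/0.0167 = 30% and 0.0125/0.0167 = 75%. Still, the effect appears capped and diagnosed hypertension is excluded (4.1.2), so a pressure stop is unlikely. A heart rate of 45 or lower is the less remote route: 3.5.4 says the pulse fell but gives no figure.

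**5. *Any* or *all*.** Read literally, the synopsis and 3.1.2 could be satisfied by one assessment within limits, which could allow escalation after a transient breach. Section 3.5.4 rules that out.

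**The case against.** The strongest reply is that withdrawal is the intended safeguard. Section 4.4 makes it an obligation, and 3.5.7 mentions the stopping criteria under the same kind of heading, so they can be read as added grounds. Clinically significant vital signs are adverse events (7.1.2, 8.1), and an event needing intervention to prevent a serious outcome can itself be serious (8.5.1). The serious branch of 4.4 needs no judgement of expectedness.

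Much of this stands. A reader might infer that the protocol has no safeguard here, or that it compels a repeat dose; the documents support neither. What remains is that 3.5.7 says only that the criteria are defined, and the section it points to says interrupt, not withdraw. Section 7.1 continues the assessments after an early infusion stop, and 8.2.2 lists interruption separately from withdrawal. The route from a numeric stop to withdrawal therefore runs through clinical judgement.

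It can also be said that 4.5 is the specific rule and the same-dose sentence only caps escalation, and that after an interrupted infusion the same dose may not mean the full planned dose. Both readings are open, but the text states neither.

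Finally, Part 1 is open-label and inpatient, with vital signs every 5 to 15 minutes through 2.5 hours, and the investigator sits on the SRC and can call it at any time. This makes an actual repeat dose improbable. It does not correct the default.

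**Conclusion.** The point holds in a narrow form. For the first patient who meets a numeric 4.5 criterion on Day 1, or on a Day 2 dose that was not raised, the written default is to repeat the dose unless the investigator withdraws the patient or the SRC, investigator or sponsor intervenes. This rests on the *all* wording of 3.5.4 and on the stop being recorded at an assessment in the 4-hour window.

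A reader might take 11% to 22% as the share of infusions at risk. It is a literal ceiling that needs a stop in the first patient (or in one patient at each of two dose levels), failed checks on both days, and nobody acting. The probability is low and cannot be computed from the documents.

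Part of section 1.3, the opening of 3.5.4, Figure 3-3 and the SRC working procedure were not available, and 3.5.4 refers in partly redacted text to an earlier patient's Day 1 dose. A further rule could lie there.

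The *any*/*all* conflict is separate and does not depend on these assumptions.

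**What to change.** 1. In the synopsis, 3.1.2 and 3.5.4, restrict the same-dose sentence to patients who failed the escalation check and met no stopping criterion in 4.5.
2. In 3.1.2 and 4.5, state that a patient with a confirmed numeric criterion, or with ischaemia or hypertensive crisis, is not dosed again at that level. The patient gets a lower dose that he or she has already tolerated, if there is one; otherwise no further dose unless the SRC agrees a lower one. It must say *lower*, because after a repeated dose the preceding dose is the same level.
3. Replace *any* with *all* in the synopsis and 3.1.2.

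Items 1 and 3 cost almost nothing. Item 2 is more open to debate: a brief bradycardia could cost the Day 3 catheterization data. Section 4.6 already provides for replacement, and on the count above this means 1 or 2 extra patients. A lower Day 2 dose would need the SRC to meet within about 24 − 2 = 22 hours of the end of the infusion, assuming the same start time each morning. No new assessments are needed.
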